5.2.2. Exclusion criteria

Exclusion criteria include:

- a) Plans to move out of the catchment area within 6 months;
- b) Participation in another research study;
- c) Unable to give informed consent.

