2.1. Specific Aims

The goal of this study is to estimate the uptake and acceptability, efficacy, and cost of methods of delivery of an intervention to reduce unhealthy drinking and HIV viral failure in a randomized controlled trial (RCT) among persons in HIV care in rural Uganda (n=270). The arms will be (1) in-person counseling during 2 quarterly clinic visits plus live booster phone calls every three weeks in the interim; (2) in-person counseling during 2 quarterly clinic visits plus tech (choice of SMS or IVR) boosters once to twice weekly in the interim; and (3) standard of care (SOC) control (brief unstructured advice, with a wait-listed intervention). We will measure outcomes as follows:

- a) **Outcome 1 is the efficacy** of an intervention to reduce unhealthy drinking and reduce HIV viral failure. This will be measured at nine months using self-report (number of drinking days in the past 21) and phosphatidylethanol (PEth), an alcohol biomarker, and viral suppression.
- b) **Outcome 2 is the uptake and acceptability** of an intervention to reduce unhealthy drinking and reduce HIV viral failure: We will examine the completion rates of the live and tech boosters, conduct post-intervention satisfaction surveys, and conduct qualitative interviews among a subsample of study participants (n=25-30) to determine acceptability and experiences with the three study arms.
- c) **Outcome 3 is the estimate of the cost of the delivery methods** of an intervention to reduce unhealthy drinking and reduce HIV viral failure: We will collect data to estimate the cost of each study arm and each mode of tech booster delivery to the patients and the clinic, including both start-up costs (e.g. initial fixed costs in tech system set-up) and maintenance costs (e.g. ongoing/recurring costs such as SMS/IVR fees, and personnel costs).

This study will be conducted in a large rural Ugandan clinic where we have 10 years of collaborative alcohol/HIV research experience. The end products of this study will be the comparisons of key outcomes to estimate effect sizes and inform the design of a future large-scale trial. The long-term aim is to implement interventions that reduce alcohol use and improve HIV outcomes feasibly and at low cost in low resource settings.

3. Background and rationale

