drink and to reduce drinking are similar to those found in other populations,¹⁰⁶ including persons with HIV,^{107,108} suggesting that interventions that were successful elsewhere can be adapted to this setting.

Feasibility of tech boosters for alcohol interventions. Drs. [name] and [name] have recently adapted the TrEAT/HWHL intervention for digital delivery (computer-based with SMS and IVR booster sessions) among sexually transmitted disease clinic patients in Baltimore (R01AA018632). Initial SMS response rates (75% of participants responded to SMS messages not requiring a response) demonstrate high engagement. [name] et al. recently developed and tested a 2-way SMS-based intervention that increased postnatal HIV clinic visits by women and their infants in Kenya.²⁹ Messages were developed and piloted within a theoretical framework, via a series of FGDs and IDIs, using a strategy similar to that proposed here.

4. Study design overview

This study is a randomized controlled trial (RCT) to compare the uptake, acceptability, cost and efficacy in reducing unhealthy alcohol use and increasing viral suppression by study arm among persons in HIV care in rural Uganda (n=270). The RCT study arms are (a) in-person counseling during 2 quarterly clinic visits plus live booster calls every 3 weeks in the interim, (b) in-person counseling during 2 quarterly clinic visits plus tech (SMS or IVR) boosters twice weekly in the interim, and (c) standard of care control (brief unstructured advice, with a wait-listed intervention). We will obtain estimates of uptake, acceptability and cost, as well as efficacy in reducing alcohol use and decreasing viral failure for each study arm. We will utilize an alcohol biomarker, phosphatidylethanol (PEth) in addition to self-report in measuring reductions in alcohol use, and we will measure viral suppression at follow up study visits (6- and 9-month visits for PEth, and 9-month visits for HIV VL). The goal is to inform the design of a future large-scale trial and, ultimately, implementation.

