The trial will be conducted during a 9-month period with the intervention occurring in the first 3 months with 6 months of follow-up. The primary outcomes will be measured 6 and 9 months post-randomization. Outcome 1 is alcohol use reduction measured by the number of drinking days (of prior 21) at 6 and 9 months. HIV viral suppression at 9 months is a secondary outcome. We will also measure intervention acceptability and uptake, as well as cost, by study arm.

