5.6. Specimen collection and laboratory procedures

DBS collection and testing. DBS collection will occur at the baseline, 6-month, and 9-month study visits. Six 50 µl drops of blood will be collected onto two Whatman 903 filter papers (3 spots each), which will be allowed to dry for ≥24 hours, and then stored packaged with a desiccant in a -80C freezer at the MUST laboratory.¹²⁷

Viral suppression: Plasma HIV viral load will be measured at baseline and 9 months using the Cepheid Xpert HIV-1 RNA assay, run on an existing GeneXpert platform in Mbarara, Uganda, that has been in use for our ongoing trials.

PEth levels: The DBS card will be tested for PEth level at the United States Drug Testing Laboratories using liquid chromatography-tandem mass spectrometry (LC/MS/MS) as described.¹²⁹ We will obtain a Materials Transfer Agreement to ship the DBS to the U.S.; no laboratories in Africa conduct this test.

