5.7. Measurements

5.7.1. Outcome variables

Efficacy analyses Outcome variables The primary outcome variable will be the number of days drinking (prior 3 weeks, TLFB) at 6 and 9 months. We chose this variable because (a) days drinking was the main outcome in the HWHL trial,¹⁶ (b) of several self-reported drinking variables, the number of drinking days was most highly correlated (Spearman $r=0.74$) with PEth level in a validation study in Uganda,⁹⁵ and (c) this variable may also be the least susceptible to bias because it does not require reporting the number of drinks, which can be challenging where non-standard drinks are common.⁹ We will use PEth level as an objective measure of prior 21-day alcohol use to confirm the findings obtained using self-report. Another main outcome variable will be HIV viral suppression at 9 months. Secondary outcomes will include the AUDIT-C score, which was associated with increased mortality in HIV-infected drinkers,¹³ and the number of heavy drinking days ($\geq 4/5$ drinks per occasion by females/males, respectively), the standard measure for pharmacotherapy trials. Other exploratory outcomes will include CD4 cell count and ART adherence.

Booster uptake and satisfaction Outcome variables Tech booster uptake will be measured from data extracted from the technology databases that record the SMS and IVR interactions. Uptake will be the proportion of sessions in which the participant answered all the questions prior to the final sign-off message; the denominator for this will be the number of tech booster sessions initiated by the system. Live booster call uptake will be tabulated from the counselor's call record forms that will be entered weekly into the study database. We will also determine the proportion of participants who request a counselor call back. We will also calculate intervention satisfaction in each arm using the Client Satisfaction Scale-8.¹⁴⁵ Among those in the tech booster arm (Arm 2), we will calculate usability via the System Usability Scale, used to evaluate new technology,^{146,147} and the proportions that chose SMS over IVR, overall and by reading literacy (yes/no).

Independent variables The predictor variable will be study arm by month (6 or 9 months).

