5.9.1. Primary analyses

Efficacy analyses

The analysis for primary outcome variable 1 (alcohol reduction) will measure the number of drinking days (of the prior 21) at six months and nine months, in pairwise comparisons of the study arms, controlling for baseline days drinking (of the prior 21).¹⁴⁹ The analyses will be conducted as intention-to-treat, and we will use Poisson or negative binomial regression for the count data, i.e. the number of drinking days at 6 and 9 months, controlling for baseline days drinking. The PEth level will be transformed to log10 PEth before analyses, based on PEth's highly skewed distribution and we will use linear regression for this outcome.

The analysis for primary outcome variable 2 (HIV viral suppression) will use logistic regression to compare the proportions with viral load<500 copies/ml, controlling for baseline viral load. We will adjust these analyses for baseline characteristics that exhibit imbalance between groups (based on a p-value ≤ 0.1 in comparisons of potential confounders listed in Table 3).

Secondary outcomes: Other exploratory outcomes will include CD4 cell count and ART adherence.

Missing data We will evaluate differences in baseline characteristics between those lost to follow-up versus those who are retained.¹⁵² If it is reasonable to assume that data are missing at random, multiple imputation methods will be applied to account for the missing data.^{152,153} We will also consider pattern mixture models,¹⁵⁴ which are applicable when the data are missing not at random.

Statistical power: With a sample size of 90 in each arm, assuming 90% 9-month retention, using a simplifying t-test for power calculations, we will have 80% power to detect a difference in the number of drinking days in the prior 21 between two study arms at nine months of ≥ 2.4 days, i.e. nearly 1 fewer day per week, as statistically significant ($\alpha=0.05$) assuming that the mean number of drinking days in the prior 21 in the control group is 7 (standard deviation is 5.5, based on prior data). Given that this is a pilot study we will not adjust for multiple comparisons.

Booster uptake and satisfaction analyses

Analyses We will calculate 95% confidence intervals for the outcomes listed above. We will conduct preliminary tests of whether the mean completion proportions and satisfaction scores differ by booster arm (live versus tech) by conducting 2-sample tests (t-test or Mann-Whitney).

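### Exclusion (a) screens out planned moves only to month 6, although the final drinking assessment and the only follow-up viral load fall at month 9

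*Combined protocol and SAP*

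**What the plan says.** Exclusion (a) in Section 5.2.2 reads "Plans to move out of the catchment area within 6 months". It is the only eligibility criterion about future moves. Inclusion (f) in Section 5.2.1 concerns where the person lives now, and inclusion (g) asks for willingness and ability to go along with the study procedures.

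The outcome schedule runs three months longer:

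- **Drinking days.** Section 4 states "The primary outcomes will be measured 6 and 9 months post-randomization". Sections 5.7.1 and 5.9.1 give the same two time points. Section 2.1 says of the efficacy outcome, "This will be measured at nine months using self-report" and other measures, and the power statement in Section 5.9.1 also refers to nine months.
- **Viral load.** Section 5.6 states "Plasma HIV viral load will be measured at baseline and 9 months", and Section 4 gives the follow-up sampling as "6- and 9-month visits for PEth, and 9-month visits for HIV VL". There is no six-month viral load.

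The standing of viral suppression varies. Section 4 says "HIV viral suppression at 9 months is a secondary outcome", Section 5.7.1 says "Another main outcome variable will be HIV viral suppression at 9 months", and Section 5.9.1 says "The analysis for primary outcome variable 2 (HIV viral suppression) will use logistic regression". That inconsistency is a separate matter. For the present point it is enough that month 9 is its only follow-up measurement under every label.

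**The concern.** The protocol already treats a planned move as a reason not to enrol someone, but the window stops three months before the last visit and no reason is given for stopping there. A person who announces at screening a move in months 7 to 9 can be randomized, and is at raised risk of missing the month-9 visit.

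The two outcomes are not equally exposed. For drinking days, the six-month value is still observed. For viral suppression, a participant who misses month 9 has only a baseline viral load. Any imputed value then rests on that baseline and on six-month correlates such as PEth, adherence, CD4 count and pill count.

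What is at stake is precision. A move already planned at screening is a pre-randomization characteristic, so 1:1:1 allocation balances it across arms in expectation, and the criterion itself gives no reason to expect an imbalance.

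**Working it through.** **Inputs from the documents (Sections 5.3 and 5.9.1).** 90 per arm; 90% retention at nine months; SD 5.5 days; difference 2.4 days; alpha 0.05 (two-sided assumed, as sidedness is not stated); and the recruitment percentages.

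**Assumed inputs.** The share of participants planning to move in months 7 to 9 is not given, so 2% and 5% are used. All of them are taken as lost, which is an upper bound. The proportion virally suppressed is not given either, so 80% and 90% are used.

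**1. The plan's own figure.** Evaluable per arm: 90 × 0.90 = 81. For a two-sample t-test the noncentrality is 2.4 / (5.5 × √(2/81)) = 2.78. This gives power of 78.8% from the noncentral t, or 79.3% from the normal approximation. The stated 80% is reproduced to rounding: the difference detectable with 80% power at 81 per arm is 2.42 days.

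**2. Movers per arm.** 90 × 0.02 = 1.8 and 90 × 0.05 = 4.5.

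**3. Two readings of the planned 10% loss.**

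- *Case A*: movers are lost in addition to the 10%. Evaluable per arm: 81 − 1.8 = 79.2, or 81 − 4.5 = 76.5.
- *Case B*: movers are already within the 10%, so screening them out recovers them. Evaluable per arm: 81 + 1.8 = 82.8, or 81 + 4.5 = 85.5.

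**4. Results.** Power is from the noncentral t at 2.4 days. The 95% confidence interval half-width for a difference in viral suppression is 1.96 × √(2p(1 − p)/n). For example, at p = 0.80 and n = 81 it is 1.96 × √(2 × 0.80 × 0.20 / 81) = 0.1232, or 12.3 points.

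| Scenario | n per arm | Power, 2.4 days | Half-width, 80% suppressed | Half-width, 90% suppressed |
|---|---|---|---|---|
| Reference | 81 | 78.8% | 12.32 points | 9.24 points |
| Case A, 2% | 79.2 | 77.9% | 12.46 | 9.34 |
| Case A, 5% | 76.5 | 76.5% | 12.68 | 9.51 |
| Case B, 2% | 82.8 | 79.7% | 12.18 | 9.14 |
| Case B, 5% | 85.5 | 81.0% | 11.99 | 8.99 |

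The largest change in power is less than 2.5 percentage points. The largest change in half-width is 12.68 − 12.32 = 0.36 points.

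**5. Room in recruitment.** The percentages in Section 5.3 give 200 × 0.95 × 0.25 × 0.85 × 0.95 × 0.70 × 0.50 × 0.85 × 0.80 = 9.13 eligible and willing people per day, against a planned 1 to 2 enrolled. If the longer window removed an assumed 5% or 10% of them, 9.13 × 0.95 = 8.7 or 9.13 × 0.90 = 8.2 per day would remain.

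**The case against.** The strongest objection is that nothing of consequence has been shown. The mover shares are assumptions, the effect is small even when every mover is lost, and the study describes itself as a pilot meant to supply effect sizes. No stated figure would change. This is right about size, and it is why the point is graded minor.

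The scenario counts also lean slightly towards a larger effect. In Case A some movers would have been among the 10% lost anyway. Treating the two losses as independent gives 81 × 0.98 = 79.4 or 81 × 0.95 = 76.95 per arm, and power of 78.0% or 76.7%. In Case B the people who replace the movers would have some attrition of their own. That gives 90 × 81/88.2 = 82.65 or 90 × 81/85.5 = 85.26 per arm, and power of 79.6% or 80.9%. These corrections are fair, but each moves power by about a quarter of a point at most.

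Other provisions already limit the loss: locator information, a month-8 reminder call, flagged charts, tracking by phone and home visit, reimbursed transport, and multiple imputation if missing at random is reasonable. Someone who leaves the catchment area might also keep attending the clinic. Inclusion (g) could be read to cover a person who already knows they cannot attend month 9, though it does not mention moving. All this reduces the expected loss but does not remove it. In particular, the documents describe no viral-load collection outside the study visits, and imputation does not replace the missing measurement.

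Finally, six months can be defended as a choice: it covers the three-month intervention and the first outcome assessment, and it keeps more mobile patients in the trial. The documents do not make that argument, but the loss of inclusiveness is a real cost of changing the criterion.

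**Conclusion.** The mismatch is plain from the text: planned moves are screened to month 6, outcomes are collected to month 9, and no other criterion covers the gap. Viral suppression is the more exposed outcome, because month 9 is its only follow-up measurement.

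The consequence is a small loss of precision, with no expected difference between arms. Its actual size cannot be computed from the documents. The figures above depend on the assumed mover shares, the assumed suppression proportions and the assumption that every mover is lost. The textual finding is firm and the magnitude is only illustrative. Severity is minor.

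**What to change.** In Section 5.2.2, change the horizon in exclusion (a) from 6 to 9 months so that it reaches the last study visit. Neither the sample size nor the power paragraph needs to change.

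The cost is one number in one criterion and a slightly narrower, less mobile eligible population. Recruitment should not suffer, since the protocol's own figures still leave several times the planned daily enrolment.

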5.2.3. Informed consent process

Informed consent process for the randomized controlled trial (RCT) will be guided by a written consent document but will in fact consist mainly of an interactive conversation between the research assistant and the potential study participant. The RA will use the informed consent document (available in Runyakole, subjected to translation, back-translation, and revision for accuracy, clarity, and ease of comprehension) as a guide to discuss all content in the document with the potential participant. After each major section and any key points, the RA will pause and check for understanding—for example, by asking the participant to repeat back, in their own words, what “the right to refuse” means. The consent form is intentionally vague in order to protect the patient-subjects (i.e. it does not mention HIV or the ISS clinic), but that the consent discussion will cover more detailed and specific information about the study, including the following key points:

- subjects are selected because they are HIV+, and identified as drinkers in a previous study or in clinic records
- the study is about developing a technology-based intervention on alcohol use among HIV+ patients
- the potential consequences of an unintentional disclosure of a participant’s HIV status because of the study

The informed consent process for both the screening and trial will take place in a private room at the ISS Clinic or research offices for the EXTEND study. The RAs will meet with eligible participants selected for recruitment to introduce the study and gauge potential subjects’ interest. Potential participants will be told the purpose of the study and the reasons that they have been approached for participation. Key points to check with the participants enrolling in the trial include:

- (1) They will be randomized to one of three arms of the study;
- (2) They will be asked to provide their name and locator information to allow the investigators to locate them for future visits;
- (3) They will be asked to bring in a support or helper person to help them with their drinking goals in the intervention;

- (4) They will receive a reminder call prior to their study visits; and
- (5) They may be asked to participate in further studies in the future.

The research assistant will explain that all information provided to study staff will be kept strictly confidential and restricted from access by anyone not involved with the study operations; that all identifying information will be kept separate from their study data (such as the transcript and voice recording from the semi-structured interview); and that all study data will be kept separately from their medical chart. Participants will be informed of the randomization process involved in an RCT and that they will not have the opportunity to choose which arm of the study they will be assigned to. Subjects will be told that they may decline to participate, may refuse to discuss any topic, and may withdraw from the study at any time. Persons unsure about participating will be encouraged to defer enrollment. When a subject agrees to participate, s/he will sign the consent form drafted. Participants will be given a copy of the consent form. If there are literacy reasons why a signature is not appropriate, individuals will be allowed to mark consent forms with an X or thumb print. The consent form includes information on how to contact the study staff to report problems or adverse events, such as violence or other harms related to disclosure that may have occurred in the study.

5.3. Enrollment and randomization

Participants will be recruited from the Mbarara ISS clinic by a clinic staff member. This person will examine clinic records to identify those who are coming in for appointments who meet these criteria: age 18 and older, on ART for at least six months (a time when alcohol consumption was found to resume),⁸⁰ reported alcohol use in the prior year at clinic entry or who reported alcohol use to research staff for other research studies being conducted at the ISS clinic. Persons meeting these pre-screening eligibility criteria will be invited to meet with a study RA. Those who agree will be screened to determine further eligibility criteria: fluency in Runyakole, living within two hours travel time from the clinic, owning or having daily access to a cell phone, and screening positive on the AUDIT-C. Although men are more likely than women to drink alcohol in Uganda,¹²⁴ two thirds of the ISS Clinic patients are women,¹⁰³ thus we expect 50% of participants to be women, as in our recent study of current drinkers at the ISS Clinic.⁸⁰ Of the 200 adult patients seen per day, 95% are on ART, and 25% report any prior year alcohol use at clinic entry. Based on our experience, we expect that 85% will accept screening, 95% will speak the appropriate language, 70% will live within two hours travel time of the clinic, 50% will test AUDIT-C positive, 85% will have cell phone access, and 80% will accept study enrollment. Thus, there will be at least 9 eligible persons per day. Due to clinic space limitations, it is very feasible to enroll 1-2 persons per day.

After eligibility is determined, we will enroll and randomize participants, to one of the three study arms, as follows:

- Arm 1: In-person counseling during 2 quarterly clinic visits plus live booster phone calls every three weeks in the interim;
- Arm 2: In-person counseling during 2 quarterly clinic visits plus tech (choice of SMS or IVR) boosters once to twice weekly in the interim;
- Arm 3: Standard of Care (SOC) control (brief unstructured advice with wait-listed intervention).

Randomization will be 1:1:1 and will be conducted by the study coordinator and the data manager (to keep the RAs blinded) using pre-printed scratch cards revealing the randomization arm, in blocks of 10 to spread out the burden of the live boosters. Those randomized to Arms 1 or 2 will be referred to the study counselor for in-person counseling and training on the booster modes. Those randomized to Arm 3 will have no contact with the study counselor.

